The study is planned to start September 1st, 2024, and will continue for two years. During the first year, the admitted patients will follow the current standard treatment pathway. After September 1st, 2025, a newly developed treatment pathway will be adhered to, and for the rest of the protocol, this pathway is described as the Fast-track pathway, as the expectation is that treatment strategy will shorten time to reduction.

All patients admitted with a dislocated THA or HA will be included in the study without prior informed consent. The patients are – disregard of cognitive status – admitted with a complication that requires acute treatment. After the acute treatment (reduction of the dislocated prosthesis), the patients are informed about the study and encouraged to participate in the second part of the study (see outcome section).

Participants

Inclusion criteria: All adult patients admitted to the Department of Emergency Medicine (Dept. of EM), University Hospital of Southern Denmark, Esbjerg, for suspected dislocated hip prosthesis who fulfills the following

- age > 18 years
- a history of either a THA or a HA in combination with at least one of the following terms:
 - having sustained a sudden, incorrect movement or twist in the hip joint in either a bending, sitting or supine position leading to inability to stand or walk
 - misalignment of the concerned lower extremity (typically shortened, with inward/outward rotation)

Exclusion criteria: Patients with

- recurrent dislocations during the same hospital admission (already “in the house”)
- anticipated difficult airway by the attending anesthesiologist
- anticipated need for extended respiratory or hemodynamic monitoring by the attending anesthesiologist
- American Society of Anesthesiologists (ASA) score > 3
- Body Mass Index (BMI) > 40
- active drug abuse
- contraindication for Propofol or Esketamine

Intervention

Referred patients will follow either the standard pathway or a newly developed fast-track pathway, specifically designed with regard of the local logistics and structure at the Dept. of EM, University Hospital of Southern Denmark, Esbjerg.

Patient reported to the coordinating nurse at the Department of Emergency Medicine, fulfilling the inclusion criteria's, without violating exclusion criteria's	
Standard Pathway (September 2024 - August 2025)	Fast-track Pathway (September 2025 - August 2026)

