Patient arrival through the ambulance entrance	Patient arrival through the ambulance entrance
Patient admitted to the Dept. of EM ward (Team 1 or 2), and transferred to a regular, standard patient bed	Patient is delivered directly to emergency trauma room no. 4 (located in conjunction of the ambulance entrance), and transferred to a radiolucent trauma bed
Patient is seen by the delegated nurse; vital parameters measured and registered, together with patient information	The orthopedic doctor AND the anesthesiologist on duty is notified and will arrive to the trauma room at their earliest convenience, depending on other acute activities
Patient is examined by one of three doctors on duty from the Dept. of Orthopedics, when	Patient is seen by the delegated nurse; vital parameters measured and registered, together with patient information, and X-ray is ordered

available (varying degree of education), and X-ray is ordered	
Patient is moved to the X-ray room (same floor level), (transfer to a special X-ray bearing is required) and will be returned to the bed ward	The diagnosis is verified by X-ray on site, by transportable X-ray machine, carried out by the radiology staff, without the need for patient transfer
Diagnosis is verified and the patient's medical files is updated	Patient's medical files is updated by the orthopedic doctor on duty (a standard paragraph will be developed for quick documentation in the medical records)
Patient is booked for a closed reduction maneuver in the operating theater during a short general anesthesia	The anesthesiologist on duty prepares for local sedation, following the sedation algorithm designed for this study, assisted by an anesthesiology nurse
Patient is reported to the anesthesiologists on duty for the purpose of planning and preparation for the anesthetic procedure	Closed reduction is completed, and control X-ray is conducted immediately on site, by transportable X-ray machine, carried out by the radiology staff, without the need for patient transfer
Patient is transferred to the operating theater, depending on other surgical activities and fasting time	Patient is transferred to the Dept. of EM ward

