As the acute treatment has been performed when the patient is asked for consent, we apply for the use of the data acquired during the acute treatment of the patient, regardless of whether they choose to participate in the secondary part of the study regarding the patient-reported outcomes, in order to not prolong the study unnecessary. This includes the patient- and prosthesis-related factors, as this will be used to control for potential residual confounding.

Sample size

Study sample size are based on the primary outcome “Time from arrival at the emergency entrance to prosthesis reduction”, applying a formula for RCT studies with clinically superiority design (21). The null-hypothesis dictates no difference in time from arrival at the emergency entrance to prosthesis reduction for patients following the Standard Pathway or the Fast-Track Pathway.

$$N = 2 \times \left(\frac{z_{1-\alpha} + z_{1-\beta}}{\delta - \delta_0} \right)^2 \times s^2$$

N = no. of patients in each group

Alpha-value = 0,05 (5% risk of type-1 error)

Beta-value = 0,90 (10% risk of type-2 error)

Delta-value (estimated true value between the two groups) \approx 4 hours

Delta₀-value (estimated clinical acceptable difference between the two groups) \approx 3 hours

S-value (pooled standard deviation (SD) for both groups) \approx 2.5 hours

A review of 16 randomly selected patients that was admitted to the University of Southern Denmark, Esbjerg, with a dislocated THA from January 2018 to May 2022 revealed a mean time from arrival at the emergency entrance to prosthesis reduction at 6 hours (range 2.7 – 9.0 hours) with a standard deviation at 1.6 hours.

$$N = 2 \times \left(\frac{1,645 \times 1,28}{4 - 3} \right)^2 \times 2,5^2 \approx 53 \text{ patients in each group}$$

Based on a review of the surgical procedures performed during the period 01.02 – 31.08.2022, we expect to admit 5-6 patients per month with a dislocated THA or HA, and we expect an attendance rate of >90% based on the primary outcome. Therefore, we will include 53 patients + 15% ≈ 60 patients in each group, due to the risk that specific comorbidities will lead to exclusion from the Fast-Track pathway by the anesthetic staff. It is thus expected that a total of 120 patients will be adhered to one of the two treatment algorithms over the course of 24 months.

Blinding

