This study concerns emergency research without the possibility of informed consent prior to intervention, and the patients will not be informed regarding their participation in a scientific study on arrival. Post-reduction, the patients are encouraged to participate in the second part of the study involving patient-reported outcome measures. The patient will not be informed of whether they have been adhered to the standard or Fast-track treatment strategy and are therefore blinded regard the treatment.

The orthopedic and anesthetic staff are not informed regarding the initiation of the current study and are therefore blinded in terms of the aim. The staff will be thoroughly instructed to adhere to the Fast-track strategy at the time for pathway shift.

Patient information

After reduction of the prosthesis, the patients are admitted to the ward at the Dept. of EM, regardless of the treatment received. During the admission, the patient will be interviewed by a dedicated study-nurse and informed about the study, without revealing the allocated treatment pathway. The rooms are single-patient only, in order to secure that the information can be given undisturbed. The patients will be screened for eligibility (cognitive status, language) for participation in the secondary part of the study, and the nurse will deliver patient information including a study overview depicting the timepoints for evaluation. When recruiting the patient for the secondary part of the project, it is stated that this is a scientific trial and that the patient has the right to have a companion present during the information. The patients are encouraged to respond before discharge, typically 12-24 hours after arrival.

Up to 15-20% of patients admitted to the hospital with a dislocated THA/HA is cognitively impaired due to dementia in a degree that hinders reasonable questionnaire response. These patients require the same acute treatment as any other patient, and there is no reason for not including them in this study. Information will be given to the patient's relatives, and we will ask for their permission to include the already obtained journal data in the study.

Patent information folder is found in the appendix (in Danish).

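### Exclusions judged by the anesthesiologist are described in use only for Fast-track, and the protocol does not settle whether the patients so diverted are analysed

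*Protocol*

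**What the plan says.** **Exclusions.** The Participants section lists "anticipated difficult airway by the attending anesthesiologist", "anticipated need for extended respiratory or hemodynamic monitoring by the attending anesthesiologist" and "contraindication for Propofol or Esketamine", next to items such as ASA > 3, BMI > 40 and recurrence within the same admission. The heading of the pathway table under Intervention, "fulfilling the inclusion criteria's, without violating exclusion criteria's", stands over both columns.

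**Timing.** In the Fast-track column the anesthesiologist is notified on arrival, before the X-ray, and then prepares the sedation. In the Standard column the anesthesiologist appears only after X-ray, confirmation and booking: "Patient is reported to the anesthesiologists on duty for the purpose of planning and preparation for the anesthetic procedure". The description of the standard anesthetic allows more extensive monitoring within that pathway at the anesthesiologist's discretion.

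**Awareness.** Blinding states: "The orthopedic and anesthetic staff are not informed regarding the initiation of the current study". Staff are to be instructed in the Fast-track strategy when the pathway changes.

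**Who is counted.** Setting says "All patients admitted with a dislocated THA or HA will be included in the study". The paragraph after the outcome list puts everyone admitted into the evaluation of the primary outcome and outcomes a-e and j-k, whatever their cognitive status. Sample size adds 15% to both groups "due to the risk that specific comorbidities will lead to exclusion from the Fast-Track pathway by the anesthetic staff".

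**Adjustment.** Age, sex, ASA score, BMI, specific comorbidities and prosthesis factors are collected to control confounding. The tests named under Statistics are unadjusted.

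**The concern.** The groups are two consecutive calendar years, so the comparison depends on the same kind of patient being counted in each. A criterion that turns on a bedside judgement does this only if the judgement is made, and recorded, in both years. Here the protocol describes it being made in one. A comorbid patient could count in the Standard year while a similar patient a year later is excluded from Fast-track and perhaps from the analysis.

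The safety aim is the most exposed. The protocol wants a faster pathway without a change in complications, readmission or mortality. Anticipated airway difficulty and need for extended monitoring mark patients prone to the airway, cardiac and pulmonary events counted in outcomes b and c. If they are removed from one year only, a pathway that raises risk could look neutral.

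**Working it through.** **Step 1: can the criteria operate alike in both years?**

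- The table heading applies the exclusions when the case is reported to the coordinating nurse. In neither column has an anesthesiologist been involved by then, so the two judged items cannot be settled at that point.
- In the Fast-track year the question arises naturally, because the anesthesiologist must decide whether to sedate in the trauma room.
- In the Standard year the anesthesiologist plans a general anesthetic. A patient needing extended monitoring, which is an exclusion under Participants, is simply treated within the pathway. Staff unaware of the study have no reason to note that an exclusion criterion was met.
- Propofol is used in both pathways and Esketamine only in Fast-track. Only the Esketamine part of the drug criterion is therefore specific to one year.

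**Step 2: are diverted patients analysed?** Setting and Outcomes say everyone admitted is included. Participants makes the judged items exclusions from the study. Sample size speaks of exclusion from the pathway, yet enlarges the sample to cover it, which is needed only if those patients are lost to the comparison. Nothing says whether a diverted patient stays in the Fast-track-year group, joins Standard or leaves.

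**Step 3: what the 15% is.** 53 × 1.15 = 60.95, which the protocol gives as 60 per group. That leaves room for (60 − 53)/60 = 7/60 = 11.7% loss. It is a planning allowance added to both groups, not an observed refusal rate. (Whether the formula yields 53 is a separate matter.)

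**Step 4: bias in time to reduction if diverted patients are dropped and their counterparts kept.** Let d be the share diverted and x the extra hours their Standard-year counterparts take. The Standard mean then carries an extra d × x that the Fast-track mean does not. The documents give neither quantity. Assumed: d = 5-15%, with 11.7% from Step 3 in between, and x = 0.5-2 h.

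| d | x = 0.5 h | x = 1 h | x = 2 h |
|---|---|---|---|
| 5% | 0.025 | 0.05 | 0.10 |
| 11.7% | 0.06 | 0.12 | 0.23 |
| 15% | 0.075 | 0.15 | 0.30 |

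The bias is about 0.03-0.30 h. For scale, the planned difference exceeds the margin by 4 − 3 = 1 h, and the standard error of the difference with SD 2.5 h and 60 per group is 2.5 × √(2/60) = 0.46 h.

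**Step 5: is a larger x plausible?** Take d = 15%, x = 4 h and the reviewed mean of 6 h. The other patients then average m, where m + 0.15 × 4 = 6, so m = 5.4 h. The diverted type averages 9.4 h, above the 9.0 h maximum among the 16 reviewed patients. That review is small and covers THA only, but it is the only evidence given.

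**Step 6: effect of counting diverted patients.** Assume they are reduced at the Standard mean of 6 h and the others at 6 − 4 = 2 h. The difference is 6 − [(1 − d) × 2 + d × 6] = 4 − 4d: 3.8 h at d = 5%, 3.53 h at 11.7% and 3.4 h at 15%.

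**The case against.** The exclusions head both columns, and every Standard patient is reported to an anesthesiologist before reduction, so some assessment takes place in both years. If the statement that everyone admitted is evaluated governs, diverted patients stay in and the bias largely disappears. ASA > 3 and BMI > 40 remove some of the frailest patients from both years. Specific comorbidities, the very reason given for the uplift, are among the intended confounders. Excluding high-risk airways is not in itself a bias, since applied equally it only defines the population.

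Much of this stands, and it limits the point. A reader might infer that the criteria cannot be applied in the Standard year, that 15% of Fast-track patients will be refused, or that mortality is visibly distorted. The documents support none of these. The criteria are formally common to both years, the 15% is an uplift to both groups, and no mortality figure by fitness for sedation is given.

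Two things remain. The Standard-year assessment comes later and asks a different question, with no plan to record the answer. And adjustment, which an analysis plan may specify in more detail, cannot recover it: the listed variables include neither the airway judgement nor a reason for diversion.

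**Conclusion.** The point holds as a conditional selection bias that the eligibility rules create and the protocol does not close. If diverted Fast-track-year patients are dropped while similar Standard-year patients are kept, the comparison is likely to favour Fast-track, most clearly for complications, readmission, mortality and length of stay. For time to reduction the bias is about 0.03-0.30 h under the assumed 5-15% diversion and 0.5-2 h excess, which is below one standard error of the difference. Its true size is unknown.

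It would go too far to call the bias established or certain in direction, because the protocol never says that diverted patients leave the analysis. It is still more than a missing detail: the passages contradict each other on who is counted, and a judgement not recorded at the bedside cannot be reliably reconstructed later.

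**What to change.** Reconcile Setting, Participants, Outcomes and Sample size as follows:

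- Define the groups by calendar period. For the primary outcome and outcomes a-e and j-k, analyse every eligible admission from September 2025 in the Fast-track group, including patients diverted to theatre.
- Keep as study exclusions only criteria that can be read identically from the record in both years, such as ASA > 3, BMI > 40 and recurrence within the same admission.
- Treat the two anesthesiologist-judged items and the sedation-drug contraindication as logged reasons for not receiving Fast-track sedation.
- Report the patients actually sedated under Fast-track as a secondary analysis.

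Clinical decisions on who is sedated are unchanged. The cost is protocol wording, one extra data field and a somewhat smaller estimated saving: under the assumption in Step 6, smaller by 0.2 h at 5% diverted and by 0.6 h at 15%. Against a 3 h margin that matters for power. With 60 per group, SD 2.5 h and a one-sided 5% test, power is about 71% for a 4 h difference, 54% for 3.8 h and 22% for 3.4 h. The sample size should therefore be checked against the redefined comparison.

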Closed reduction is completed during a short general anesthesia, often with simultaneous muscle relaxation. Patient is transferred back and forth to a surgical bearing to confirm reduction, using a C-arm X-ray (not useful for documentation)	Patient is seen by a physiotherapist and mobilized with/without walking aids
Patient return to the Dept. of EM bed ward	Patient is discharged with/without a planned outpatient follow-up by a hip surgeon, depending on the specific patient case
Patient is moved to the X-ray room for a control X-ray (same floor level), (transfer to a special X-ray bearing is required) and will be returned to the bed ward	
Patient is seen by a physiotherapist and mobilized with/without walking aids	

Patient is discharged with/without a planned outpatient follow-up by a hip surgeon, depending on the specific patient case	
--	--

Assumed fast-track advantages includes

- elimination of several patient transfers back and forth from the Dept. of EM bed ward to X-ray rooms and operating theater (saves **time** and **hospital resources**)
- elimination of several patient transfers between different beds (reduces **patient pain** and **discomfort**)
- hip reduction in sedation rather than general anesthesia disregard of fasting time, - safely administered by anesthesiologists rather than by the orthopedic (saves **time**, increases **safety**)

Detailed description of standard anesthetic procedure for patients enrolled for standard pathway hip reduction (current practice)

Patients following the standard pathway and local guidelines, will receive a general anesthesia with a rapid sequence induction and intubation using Propofol 1-2 mg/kg, Alfentanil 0,2-0,3 mg/kg or Fentanyl 2-3 µg/kg and Suxamethonium 1 mg/kg. The patient is as a standard monitored with non-invasive blood pressure, saturation, pulse, 3-point ECG and end-tidal CO₂. More extensive monitoring may be used if considered necessary by the attending anesthesiologist.

Detailed description of new fast-track sedation procedure for patients enrolled for fast-track hip reduction

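### Patients are called blinded to treatment because the pathway name is withheld, yet they experience the pathway directly; staff blinding to the aim is doubtful once the new pathway starts

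*Protocol*

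**What the plan says.** The Blinding section makes two separate claims.

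- **Patients.** They will not be told whether they followed the standard or the Fast-track strategy, and they "are therefore blinded regard the treatment".
- **Orthopedic and anesthetic staff.** They "are not informed regarding the initiation of the current study and are therefore blinded in terms of the aim". The next sentence adds: "The staff will be thoroughly instructed to adhere to the Fast-track strategy at the time for pathway shift".

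Under Setting, the two pathways run one after the other: standard care in the first year from September 2024, the new pathway from September 2025. The Patient information section has a study nurse tell patients about the study after reduction, without disclosing their pathway. The Outcomes section lists 11 secondary outcomes, a to k. Of these, f to i are hip pain on a numeric rating scale, HOOS, EQ-5D and patient satisfaction. The same section allows a patient to be included more than once.

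**The concern.** Blinding to treatment means that the person cannot tell which treatment was given. The protocol infers it from something weaker, namely that nobody names the pathway to the patient. If the two pathways feel different, the stated property is absent.

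Outcomes f to i are the patient's own ratings and are open to expectation and to the experience of care. A reader who takes the Blinding section at face value would credit them with a protection that they lack. For staff, the issue is whether unawareness of the aim can last equally through both periods. Pathway and calendar period coincide completely, so any change in staff awareness at the shift cannot be separated from the change of pathway.

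**Working it through.** No figure in the protocol is at issue and no arithmetic applies beyond a count of outcomes. The check sets the Blinding section beside the description of care.

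**1. What the patient experiences** (Intervention table and the two anesthetic descriptions)

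| Step | Standard pathway | Fast-track pathway |
|---|---|---|
| Arrival | Ward bed in the emergency department | "Patient is delivered directly to emergency trauma room no. 4" |
| Diagnostic X-ray | Moved to the X-ray room and back | Mobile X-ray where the patient lies |
| Reduction | "Patient is booked for a closed reduction maneuver in the operating theater during a short general anesthesia" | In the same trauma room |
| Anesthesia | Patients "will receive a general anesthesia with a rapid sequence induction and intubation" | "The anesthesiologist on duty prepares for local sedation, following the sedation algorithm designed for this study" |
| Control X-ray | Second trip to the X-ray room | Mobile X-ray on site |

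The protocol itself lists fewer transfers, with less pain and discomfort, among the assumed advantages of the new pathway. A difference that is meant to be felt cannot also be hidden from the person who feels it.

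**2. What withholding the name can achieve.** Within each year, eligible patients follow one pathway, and they hear of the study only after reduction. A patient admitted once may not know that another pathway exists, or which is new or expected to be better. That is possible masking to the label or the hypothesis. It is not blinding to treatment.

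**3. Where even that is weak.** Repeat inclusion is allowed and the number of previous dislocations is recorded. Some patients may know the standard pathway from an earlier admission, or be included in both periods, and can compare the two.

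**4. Staff, first year.** They give usual care and are not told that a study has begun. Nothing in the protocol contradicts unawareness of the aim in this period.

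**5. Staff, from September 2025.** They are thoroughly instructed in a new pathway and follow a sedation algorithm made for the study. They necessarily know which treatment they give, and they may well infer why it was introduced. Unawareness of the aim is doubtful here, and it may differ between the two periods.

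**6. Reach.** Outcomes f, g, h and i are 4 of the 11 secondary outcomes. Between them they serve the three secondary aims in the Background: hip function and quality of life, pain, and satisfaction. The primary outcome, arrival-to-reduction time, is a clock time and not a patient rating. It is exposed only through step 5, if staff who know the aim act faster for that reason.

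**The case against.** The strongest defence is that this is largely terminology. The protocol states its mechanism openly (the label is not disclosed), and most patients may have no basis for comparison. It calls the study an observational cohort following STROBE, and neither the sample size nor any planned test relies on blinding. Satisfaction is also meant to capture the care experienced. Much of the difficulty in crediting a pain difference to speed alone comes from the pathway being a bundle, and relabelling will not change that. All of this stands, and it keeps the point minor. It does not rescue the sentence that patients are blinded to the treatment.

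A reader might be tempted to go further in four ways that the protocol does not support.

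- **That both forms of blinding are impossible.** For staff, the claim concerns the aim and not the treatment. It is uncontradicted in the first year. In the second it is doubtful, not impossible: a new pathway can be introduced as ordinary practice, and the protocol adopts the Fast-track name as its own convention without clearly saying what staff will hear.
- **That results would be presented as blinded.** No section says so.
- **That the study nurse's blinding is broken.** No section claims that the nurse is blinded, and the nurse's help is already limited to cases of need during the admission.
- **That the patient information is slanted.** The folder is an appendix that is not shown, so its content cannot be judged.

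**Conclusion.** The point holds in a limited form. The statement that patients are blinded to treatment is not supported by the protocol's own description of care; patients are at most unaware of the label or the hypothesis. Staff unawareness of the aim is plausible in the first year and doubtful from September 2025, so it may be unequal between the periods.

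The consequence is confined mainly to the four patient-reported outcomes f to i, with a possible smaller effect on the primary time outcome through staff behaviour. The direction and size of any bias cannot be derived from the document. The conclusion rests on two assumptions: that care is delivered as the pathway table describes, and that patients can perceive differences in room, transfers and anesthesia. It does not depend on what the patient folder says. This is a minor correction that leaves the design, sample size and analysis unchanged.

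**What to change.** Replace the two blinding claims with a statement of this kind: *Patients and treating staff are not blinded to the pathway. Patients are not told the pathway label, and staff are not informed of the study in the first year.* Add that the patient-reported outcomes f to i are open-label and will be interpreted with that limitation.

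The cost is wording only; no procedure, sample size or analysis changes. The downside is that the stated protection against bias becomes less favourable, which reflects the design as it is.
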